4.3. Randomization Criteria

Eligible subjects will be randomized in a 1:1 allocation ratio to receive either tofacitinib 5 mg BID or 10 mg BID at baseline of Study A3921288. Subjects will be stratified at baseline based on the endoscopic subscore (0 versus 1) of their most recent endoscopy.

4.4. Lifestyle Requirements

4.4.1. Tobacco

Smoking can have an influence on the severity of UC symptoms. For that reason, subjects should discuss with the study investigator if they wish to make changes to their smoking habits during the study. Use of nicotine patch should be recorded as a concomitant medication.

4.4.2. Diet and Dietary Supplements

Subjects are encouraged to keep their diet habits constant throughout the study. It is recommended that subjects avoid consumption of grapefruit juice exceeding 8 ounces (~240 mL) total in a day while in the study.

For the purposes of this protocol, dietary supplements, such as vitamins, minerals, purified food substances, and herbals with pharmaceutical properties are considered as concomitant medications. Dietary supplements and herbs are allowed in the study, provided they are taken at stable doses prior to the baseline visit if they are started prior to study entry, and not associated with known effects on CYP3A that may impact on metabolism of the investigational product. Starting dietary supplements or herbs during the study as a new medication is permissible as long as they are not listed on the prohibited medication list (see [Appendix 3](#)).

4.4.3. Vaccination

Vaccination with live components is prohibited during the study and for 6 weeks after last dose of investigational product. Similarly, current routine household contact with individuals who have been vaccinated with live vaccine components should be avoided during treatment and for 6 weeks following completion of study treatment. Following vaccination with live component vaccines, the virus may be shed in bodily fluids, including stool, and there is a potential risk that the virus may be transmitted.

Some examples of live or attenuated vaccines include but are not limited to: FluMist® (intranasal influenza vaccine), attenuated rotavirus vaccine, varicella vaccine, attenuated typhoid fever vaccine, oral polio vaccine, and Zostavax® (zoster vaccine).

4.4.4. Contraception

Based on preclinical data, tofacitinib has a potential risk of teratogenicity and early fetal loss. Due to this potential risk, female subjects of childbearing potential should not be administered tofacitinib until pregnancy is excluded.

Female subjects of nonchildbearing potential must meet at least 1 of the following criteria:

- a. Achieved postmenopausal status, defined as follows: cessation of regular menses for at least 12 consecutive months with no alternative pathological or physiological cause; status may be confirmed with a serum follicle-stimulating hormone (FSH) level confirming the postmenopausal state;
- b. Have undergone a documented hysterectomy and/or bilateral oophorectomy;
- c. Have medically confirmed ovarian failure.

All other female subjects (including female subjects with tubal ligations) are considered to be of childbearing potential.

All female subjects who are of childbearing potential as applicable to the study who are, in the opinion of the investigator, sexually active and at risk for pregnancy with their partner(s) must agree to use a highly effective method of contraception consistently and correctly for the duration of the active treatment period and for at least 28 days after the last dose of investigational product. The investigator or his or her designee, in consultation with the subject, will confirm that the subject has selected an appropriate method of contraception for the individual subject from the permitted list of contraception methods (see below) and will confirm that the subject has been instructed in its consistent and correct use. At time points indicated in the [Schedule of Activities](#), the investigator or designee will inform the subject of the need to use highly effective contraception consistently and correctly and document the conversation and the subject's affirmation in the subject's chart (subjects needs to affirm their consistent and correct use of at least 1 of the selected methods of contraception). In addition, the investigator or designee will instruct the subject to call immediately if the selected contraception method is discontinued or if pregnancy is known or suspected in the subject or the partner.

Highly effective methods of contraception are those that, alone or in combination, result in a failure rate of less than 1% per year when used consistently and correctly (ie, perfect use) and include the following:

1. Established use of hormonal methods of contraception associated with inhibition of ovulation (eg, oral, inserted, injected, implanted, transdermal) provided the subject or male subject's female partner plans to remain on the same treatment throughout the entire study and has been using that hormonal contraceptive for an adequate period of time to ensure effectiveness.
2. Correctly placed copper-containing intrauterine device (IUD).
3. Male condom or female condom used WITH a separate spermicide product (ie, foam, gel, film, cream, or suppository). For countries where spermicide is not available or condom plus spermicide is not accepted as highly effective contraception, this option is not appropriate. Note: This option is not appropriate or accepted in the European Union (EU); an alternate form of contraception must be selected.
4. Male sterilization with absence of sperm in the post-vasectomy ejaculate.
5. Bilateral tubal ligation/bilateral salpingectomy or bilateral tubal occlusive procedure (provided that occlusion has been confirmed in accordance with the device's label).

NOTE: Sexual abstinence, defined as completely and persistently refraining from all heterosexual intercourse (including during the entire period of risk associated with the study treatments) may obviate the need for contraception ONLY if this is the preferred and usual lifestyle of the subject.

Subjects in Canada who are females of childbearing potential and sexually active must use two contraceptive methods at the same time: one highly effective contraceptive method and one additional effective contraceptive method as described below.

Highly effective contraceptive methods may include hormonal contraceptives (eg, combined oral contraceptives, patch, vaginal ring, injectables, and implants), intrauterine device (IUD) or intrauterine system (IUS), vasectomy or tubal ligation.

Effective methods may include barrier methods of contraception (eg, male condom, female condom, cervical cap, diaphragm or contraceptive sponge). The proper use of diaphragm or cervical cap includes use of spermicide and is considered one barrier method. The cervical cap and contraceptive sponge are less effective in parous women. The use of spermicide alone is not considered a suitable barrier method for contraception.

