4.4.6. Surgery

During the course of this study, no elective surgery should be scheduled without first consulting with the Pfizer medical monitor. Investigators should contact the Pfizer medical monitor regarding subjects who undergo non-elective surgery to discuss their suitability to remain in the study.

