5.8. Concomitant Medication(s)

All subjects will be questioned about concomitant medication use at each study visit. In addition, the following concomitant medications that the subject had been taking from Study A3921139 and will continue to take in this study will be recorded:

Table 2. Concomitant Medications

Treatment Type	Information Recorded	Recording Period
Ulcerative colitis (UC)	Daily dose, unit, frequency, route, start and stop dates	Treatment period Follow-up period
Lipid lowering agents	Daily dose, unit, frequency, route, start and stop dates	Treatment period Follow-up period
Anti-hypertension agents	Start and stop dates	Treatment period Follow-up period
Anti-diabetic agents	Start and stop dates	Treatment period Follow-up period
All other medications*	Indication, start and stop dates	Treatment period Follow-up period

* Includes nonprescription drugs, vitamins, and dietary supplements.

The following therapies for the treatment of UC are allowed:

- Oral 5-aminosalicylic acid (5-ASA) or sulfasalazine.

Subjects receiving either concomitant combined hormonal contraceptives or hormone replacement therapy must have their tofacitinib dose adjusted to open-label 5 mg BID.

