Once the subject is confirmed to meet the definition for flare, documented by site read endoscopy, the investigator may adjust the dose through the IRT system provided that the subject does not have any of the risk factors for venous thromboembolism (see [Section 7.3.6](#)). Once confirmed by the investigator, subjects may have a dose increase to 10 mg BID or remain on 10 mg BID, depending on their initial treatment assignment. Dose adjustments for confirmed flare will not be permitted prior to the Month 1 study visit.

Subjects who develop one or more of the risk factors for venous thromboembolism during the study will not be permitted to increase their tofacitinib dose to 10 mg BID should they experience a flare of their UC.

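### Nothing asks a subject to tell the site before starting a combined hormonal contraceptive or HRT between visits, so a woman on 10 mg BID could take a barred combination until the next check

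*Protocol*

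**What the plan says.** **The call instruction.** In Protocol 4.4.4 the investigator or designee is to "instruct the subject to call immediately if the selected contraception method is discontinued or if pregnancy is known or suspected". That gives two triggers: stopping the chosen method, and pregnancy. The instruction is addressed to women of childbearing potential.

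**The dose rule.** Protocol 5.8 states: "Subjects receiving either concomitant combined hormonal contraceptives or hormone replacement therapy must have their tofacitinib dose adjusted to open-label 5 mg BID". Section 7.3.6 puts the same products on its list of risk factors for venous thromboembolism (VTE) and does not permit 10 mg BID once a new factor is identified. Under 5.11, a subject who develops a listed factor "will not be permitted to increase their tofacitinib dose to 10 mg BID should they experience a flare of their UC".

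**When new use is looked for.** The risk factor check (7.3.6) and the questions on concomitant medication (5.8) take place at each study visit. During the pandemic, Appendix 9 places the risk check before further dispensing.

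**The contraception lists.** Item 1 of the permitted methods in 4.4.4 is "Established use of hormonal methods of contraception associated with inhibition of ovulation", on condition that the user plans to stay on the same treatment. The paragraph for Canada is more explicit: "Highly effective contraceptive methods may include hormonal contraceptives (eg, combined oral contraceptives, patch, vaginal ring, injectables, and implants". Neither place mentions VTE or refers to 5.8, 5.11 or 7.3.6.

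**The concern.** Starting a hormonal product is a voluntary act that the subject knows about in advance. That sets it apart from most other entries on the 7.3.6 list, such as heart failure or a thrombosis. The protocol also treats a risk factor as urgent once it is known: Section 3 asks the subject to come back to the site promptly for the 5 mg supply. But no available section asks the subject to tell the site about a new start between visits.

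Three kinds of start could be missed until the next visit:

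- HRT in a postmenopausal woman, whom the 4.4.4 instruction does not address;
- a combined product added for a non-contraceptive reason;
- a new contraceptive method taken up without first being discussed with the site.

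At stake is a period on 10 mg BID together with a product that the protocol says must bring the dose down to 5 mg BID. An early warning would also help the subject. Before starting, she could choose another listed method, such as a copper IUD, and keep her assigned dose.

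**Working it through.** The plan gives no figure on this point, so there is none to reproduce. The check has two parts.

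**1. Which changes prompt contact between visits?**

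- *Stops the chosen method, including a switch to a combined product:* the 4.4.4 trigger is met, so a call is due.
- *Pregnancy known or suspected:* the 4.4.4 trigger is met, so a call is due.
- *Adds a combined product while keeping the chosen method, or takes one for another indication:* no trigger.
- *Postmenopausal woman starts HRT:* outside the 4.4.4 instruction, and 5.8 sets no duty to report between visits.

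**2. How long could the combination last before a required check?**

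Inputs: the SAP Appendix 1 target days, which from Month 6 run 180, 270, ... to 1260, and the ±7-day visit window in the Protocol Schedule of Activities. Footnote 11 of that schedule says that all subjects were enrolled and past Month 6 by Amendment 3, so the later intervals are the relevant ones.

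- Nominal interval: 270 − 180 = 90 days. Every later interval is the same.
- Shortest, with the first visit 7 days late and the next 7 days early: 90 − 14 = 76 days.
- Longest, with the first visit 7 days early and the next 7 days late: 90 + 14 = 104 days.

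Assume that the start falls uniformly over an interval of length L and that nothing brings it to the site sooner. The mean time to the next check is then L/2:

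- L = 76: 38 days
- L = 90: 45 days
- L = 104: 52 days

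The 104-day case needs a start just after an early visit, a late next visit and no contact in between.

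**Who is exposed.** Protocol 4.3 allocates 1:1, so about half of the women who start such a product would have been assigned 10 mg BID, plus any escalated from 5 mg BID after a flare. A woman on blinded 5 mg BID would have her move to the open-label supply delayed, but her dose is already the permitted one. The documents do not say how many women start such products or how many subjects are in Canada.

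**The case against.** The strongest reply is that visit-based detection is the stated design and applies equally to every VTE risk factor. Each treatment visit after baseline combines a contraception check (for women of childbearing potential), a medication review and a risk check, and unplanned visits are allowed. Section 4.4.4 also has the investigator confirm, together with the subject, that a suitable method has been chosen, and that investigator is bound by 5.8 and 7.3.6. Outside Canada, item 1 covers established use only. Subject-facing consent material is not in the public copy and may say more. All of this lowers the risk. None of it makes the subject report before starting, and none of it deals with HRT or non-contraceptive use between visits.

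Three stronger readings are tempting, and the documents do not support them.

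- *That 4.4.4 contradicts the VTE rules by listing combined products.* It does not. Section 5.8 allows these products with open-label 5 mg BID, so listing them as contraception is correct. What is missing is a cross-reference.
- *That a woman in Canada who ends abstinence can start a combined pill with no site contact while following the text exactly.* Abstinence "may obviate the need for contraception ONLY if this is the preferred and usual lifestyle of the subject", and once she is sexually active the rule is: "Subjects in Canada who are females of childbearing potential and sexually active must use two contraceptive methods at the same time". But she then enters the group whose method the investigator confirms in consultation with her, and ending abstinence can fairly be read as stopping the arrangement that was agreed. The route is open only if the consultation does not happen before she starts.
- *That the surgery section shows a VTE safeguard that 4.4.4 failed to match.* Section 4.4.6 says: "During the course of this study, no elective surgery should be scheduled without first consulting with the Pfizer medical monitor". That is a general rule on elective surgery and does not mention VTE.

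**Conclusion.** The point stands as a gap in reporting between visits, not as a gap in the dose rule, which is complete and mandatory. After Month 6, a woman on 10 mg BID who begins a combined hormonal contraceptive or HRT unannounced could take both for 45 days on average (38 to 52 across the window range), and for 104 days at most if visits are kept. These figures rest on a start at a random time and on no earlier contact. The number of women concerned is unknown and may be zero.

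Severity is low and the change is optional. A reader might infer that efficacy results are affected, but they are not. SAP 5.3.3 records that no subject had a dose reduction before Month 6 and that its reduction rules are not used in the primary analysis. For the final analysis, those rules work from the date of the dose change and need no amendment.

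**What to change.** - **In 5.8**, so that all women are covered, including HRT users of nonchildbearing potential, add an instruction along these lines: *subjects are to contact the site before starting or adding a combined hormonal contraceptive or HRT, for any reason.*
- **In the 4.4.4 call instruction**, add the same trigger beside the two that are there.
- **In item 1 and the Canada paragraph of 4.4.4**, note that combined products require open-label 5 mg BID and rule out escalation for flare, with a reference to 5.8, 5.11 and 7.3.6.

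The instruction should go to every woman in the study whatever her arm, because the initial assignment is blinded. The cost is a clarification letter and a few extra calls. The dose rule, the CRF and the SAP stay as they are.

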4.4.5. Reproductive Status of Male Subjects

No tofacitinib effects on male fertility or offspring of dosed males have been observed in any preclinical studies conducted to date. Therefore, no specific contraceptive measures are required in male subjects during study participation.

4.4.6. Surgery

During the course of this study, no elective surgery should be scheduled without first consulting with the Pfizer medical monitor. Investigators should contact the Pfizer medical monitor regarding subjects who undergo non-elective surgery to discuss their suitability to remain in the study.

4.5. Sponsor's Qualified Medical Personnel

The contact information for the sponsor's appropriately qualified medical personnel for the study is documented in the study contact list located in the study portal.

To facilitate access to appropriately qualified medical personnel on study-related medical questions or problems, subjects are provided with a contact card. The contact card contains, at a minimum, protocol and investigational product identifiers, subject study numbers, contact information for the investigator site, and contact details for a contact center in the event that the investigator site staff cannot be reached to provide advice on a medical question or problem originating from another healthcare professional not involved in the subject's participation in the study. The contact number can also be used by investigator staff if they are seeking advice on medical questions or problems; however, it should be used only in the event that the established communication pathways between the investigator site and the study team are not available. It is therefore intended to augment, but not replace, the established communication pathways between the investigator site and the study team for advice on medical questions or problems that may arise during the study. The contact number is not intended for use by the subject directly, and if a subject calls that number, he or she will be directed back to the investigator site.

5. STUDY TREATMENTS

For the purposes of this study, and per International Council for Harmonisation (ICH) guidelines, investigational product is defined as a pharmaceutical form of an active ingredient or placebo being tested or used as a reference/comparator in a clinical trial, including a product with a marketing authorization when used or assembled (formulated or

packaged) in a way different from the approved form, or when used for an unapproved indication, or when used to gain further information about an approved use (ICH E6 1.33).

For this study, the investigational product is tofacitinib.

Subjects will be randomized to one of two dosing groups at baseline of Study A3921288:

- Tofacitinib 5 mg BID.
- Tofacitinib 10 mg BID.

Subjects who meet the protocol definition for flare may have a dose increase to 10 mg BID or remain on 10 mg BID, depending on their initial treatment assignment (see [Section 5.11](#)), provided that the subject does not have any of the risk factors for venous thromboembolism (see [Section 7.3.6](#)).

5.1. Allocation to Treatment

Allocation of subjects to treatment groups will proceed through the use of an interactive response technology (IRT) system (interactive Web-based response [IWR]). The site personnel (study coordinator or specified designee) will be required to enter or select information including but not limited to the user's identification (ID) and password, the protocol number, and the subject number. The site personnel will then be provided with a treatment assignment, randomization number, and container number(s) when investigational product is being supplied via the IRT system. The IRT system will provide a confirmation report containing the subject number, randomization number, and container number(s) assigned. The confirmation report must be stored in the site's files.

The study-specific IRT reference manual will provide the contact information and further details on the use of the IRT system.

5.2. Breaking the Blind

The study will be subject and investigator blinded to the initial treatment assignment at baseline.

At the initiation of the study, the investigator site will be instructed on the method for breaking the blind. The method will be an electronic process. Blinding codes should be broken only in exceptional circumstances when knowledge of the actual treatment code is absolutely essential for further management of the subject. If an investigator believes that immediate unblinding is necessary and time and circumstances allows, he/she is encouraged to discuss with a member of the study team. However, discussion with a member of the study team in advance of the unblinding is not required. When the blinding code is broken, the reason must be fully documented and entered on the case report form (CRF).

5.3. Subject Compliance

Investigational product compliance will be assessed by the site at each study visit starting at the visit after the baseline visit (Month 1) up to the end of treatment. Non-compliance is defined as taking less than 80% or more than 120% of study drug products as directed by the dosing instructions. Subjects are to bring the study drug bottle(s) with any remaining study drug and any empty bottle(s) to each visit for review. The investigator has the discretion to withdraw any subject from the study for reasons of non-compliance with the dosing regimen. Investigators should indicate on the appropriate CRF page noncompliance with study treatment and provide an explanation. Inventory control of all investigational products must be rigorously maintained throughout the duration of the study until all medication has been accounted for and/or returned to the sponsor. Any discrepancies noted between drug dispensing records and the drug inventory must be reported to Pfizer.

5.4. Investigational Product Supplies

5.4.1. Dosage Form(s) and Packaging

Blinded tofacitinib and its matched placebo will be provided as tablets for oral administration. The 5-mg tablets and their matching placebos will be supplied in separate bottles and labeled according to local regulatory requirements.

